## **6.6. Interim Analyses and Data Monitoring**

No formal statistical interim analysis based on the safety data is planned. The SRC will review safety data through seven days after the last sentinel participant is vaccinated before proceeding to vaccinate additional participants in each cohort. The SRC will review safety data, which may include solicited and unsolicited AE/SAEs, concomitant medications, clinical laboratory values, vital signs, and any physical examinations, through Day 64 for each cohort prior to dose escalation.

No interim immunogenicity review is planned.

## **6.7. Multicenter Studies**

Not applicable. This is a single center study.

## **6.8. Multiple Comparisons/Multiplicity**

The primary outcome is descriptive. No testing or adjustments for multiple testing are planned.

## 7. STUDY PARTICIPANTS

### 7.1. Disposition of Participants

[Table 11](#) will present a summary of the reasons that participants were screened but not enrolled.

The composition of analysis populations, including reasons for participant or visit exclusion, by treatment group, will be presented in [Table 9](#).

The disposition of participants in the study including the number of participants screened, enrolled/randomized, receiving vaccination 1, receiving vaccination 2, receiving vaccination 3, completing the final blood draw, completing follow-up, and contributing both pre- and at least 1 post-vaccination blood sample will be tabulated by treatment group ([Table 8](#)).

A flow diagram showing the disposition of study participants, adapted from the CONSORT Statement [19] will be included ([Figure 1](#)). This figure will present the number of participants screened, enrolled, discontinued, terminated early (including lost to follow-up), and analyzed, by treatment group.

A listing of participants who discontinued vaccinations or terminated from study follow-up and the reason will be included in [Listing 2](#).

### 7.2. Protocol Deviations

All protocol deviations will be classified as major or minor using the definitions below.

- Major Deviation – A deviation from the Institutional Review Board-approved protocol documents that have, or may have the potential to, negatively impact the rights, welfare, or safety of the participant, or to substantially negatively impact the scientific integrity or validity of the study.
- Minor Deviation – A deviation that does not have the potential to negatively impact the rights, safety, or welfare of participants or others, or the scientific integrity or validity of the study.

Prior to database lock, the SDCC will provide a listing of all protocol deviations with an initial classification of major or minor to DMID who will review and make final determinations to be included in the database lock.

A summary of participant-specific protocol deviations will be presented by deviation category, deviation type, and treatment group for all participants ([Table 4](#)). All participant-specific protocol deviations and non-participant-specific protocol deviations will be presented in data listings ([Listing 3](#) and [Listing 4](#), respectively).

## **8. EFFICACY EVALUATION**

Not applicable.

## 9. SAFETY EVALUATION

### 9.1. Demographic and Other Baseline Characteristics

All summaries and analysis of safety data will be presented for the Safety Population.

Summaries of categorical (sex, ethnicity, and race) and continuous (age, height, weight, and BMI) demographic variables will be presented by treatment group and overall ([Table 12](#) and [Table 13](#) respectively). Ethnicity is categorized as “Hispanic or Latino” or “Not Hispanic or Latino”. In accordance with NIH reporting policy, participants may self-designate as belonging to more than one race or may refuse to identify a race, the latter reflected in the eCRF as “No” to each racial option.

Individual participant demographics and baseline characteristics are included in [Listing 6](#).

#### 9.1.1. Prior and Concurrent Medical Conditions

All current illnesses and past pre-existing medical conditions will be coded using the Medical Dictionary for Regulatory Activities (MedDRA®) dictionary version 27.0 or higher.

Summaries of participants’ pre-existing medical conditions will be presented by MedDRA SOC and treatment group ([Table 14](#)).

Individual participant listings of pre-existing and concurrent medical conditions will be presented ([Listing 7](#)).

#### 9.1.2. Prior and Concomitant Medications

Medications (prescription and over-the counter) and non-study vaccinations taken 30 days prior to enrollment through 28 days after the final vaccination or early termination, whichever occurs first, will be classified using the World Health Organization (WHO) Drug Dictionary (March 2024) Anatomical Therapeutic Chemical (ATC) Classification Levels 1 and 2 and summarized by treatment group and overall ([Table 98](#)).

Individual participant listings of all prior and concomitant medications will be presented ([Listing 16](#)).

### 9.2. Measurements of Treatment Compliance

The number participants receiving at least one vaccination, as well as those receiving all scheduled vaccinations, will be presented by treatment group as part of the participant disposition table ([Table 8](#)).

[Table 10](#) presents the dates of first vaccination by treatment group and overall. A listing of participants receiving investigational product will be presented in [Listing 1](#).

### 9.3. Adverse Events

When calculating the incidence of adverse events (i.e., on a per participant basis), each participant will only be counted once per AE using the event with maximum severity and any repetitions of adverse events within a participant will be ignored; the denominator will be the total number of participants receiving the specified vaccination. All unsolicited adverse events reported will be included in [Listing 11](#).

An overall summary of adverse events will be presented in [Table 30](#). A table of all SAEs and non-serious AEs occurring in at least 5% of participants in any treatment group will be presented by MedDRA SOC and PT and treatment group in [Table 31](#).

### 9.3.1.     Solicited Events and Symptoms

Temperatures collected on the Vital Signs eCRF within 7 days following vaccination will be considered towards the solicited AE of fever and will be included in all tables, figures, and listings summarizing solicited AEs.

The number and percentage with 95% CI of participants reporting at least one solicited adverse event of at least mild severity within 7 days following vaccination will be summarized for each solicited symptom, any systemic symptom, any local symptom, and any symptom following each vaccination and following any vaccination for Cohort 1 ([Table 32](#)), Cohort 2 ([Table 33](#)), and Cohort 3 ([Table 34](#)). The 95% CI will be calculated using Clopper-Pearson methodology from a binomial distribution (SAS Proc Freq with a binomial option).

For each systemic and local symptom, any systemic symptom, any local symptom, and any solicited symptom, the number and percentage of participants reporting the symptom will be summarized by severity for each day and maximum severity within 7 days after each vaccination for Cohort 1 for vaccination 1 ([Table 35](#)), vaccination 2 ([Table 36](#)), vaccination 3 ([Table 37](#)), and any vaccination ([Table 38](#)). Analogous tables for each vaccination and any vaccination will be presented for Cohort 2 ([Table 39](#), [Table 40](#), [Table 41](#), and [Table 42](#)) and Cohort 3 ([Table 43](#), [Table 44](#), [Table 45](#), and [Table 46](#)). For each event the denominator is the number of participants with non-missing data for the specific event.

The percentage of participants reporting any solicited systemic symptom will be summarized graphically in a bar chart by maximum severity, day post vaccination, and vaccination group for each vaccination ([Figure 32](#), [Figure 33](#), and [Figure 34](#)) and for all vaccinations combined ([Figure 35](#)). Analogous figures will be presented for any solicited local symptom ([Figure 36](#), [Figure 37](#), [Figure 38](#), and [Figure 39](#)).

The percentage of participants experiencing each solicited symptom within 7 days of vaccination will be summarized in a bar chart by maximum severity and treatment group for each vaccination ([Figure 40](#), [Figure 41](#), and [Figure 42](#)) and for all vaccinations combined ([Figure 43](#)).

All solicited adverse events will be presented by participant in [Listing 9](#) for systemic symptoms and [Listing 10](#) for local symptoms.

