### 4.4.5. Selection and Timing of Dose for Each Participant

All participants will receive three doses of vaccine on Days 1, 29, and 57. A fixed dose of CJCV2 will be used for each cohort: 1  $\mu$ g in Cohort 1, 3  $\mu$ g in Cohort 2, and 10  $\mu$ g in Cohort 3. Any participant assigned to receive ALFQ will receive the same fixed dose (200  $\mu$ g 3D-PHAD and 100  $\mu$ g QS-21). Participants in each cohort will be randomized using a 1:1 allocation ratio to receive either CJCV2 alone or CJCV2+ALFQ.

Sentinels will be dosed at least two hours apart with no more than two sentinels per day vaccinated.

Between the time of vaccination of the first six sentinels to 7 days after enrollment of the last sentinels, no new participants will be vaccinated, but screening may continue.

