## 9.7. Vital Signs and Physical Evaluations

Vital sign measurements will include systolic blood pressure, diastolic blood pressure, pulse, and oral temperature. Vital signs will be assessed at screening (Day -30 to -2), Day 1, Day 8, Day 29, Day 36, Day 57,

Day 64, Day 85, and Day 113 for all Cohorts. Cohort 1 was enrolled and completed follow-up under protocol v4.0 (25MAY2022) which also required collection of vital signs at Day 3, Day 15, Day 31, Day 43, Day 59, and Day 71; in the later versions of the protocol followed by Cohorts 2 and 3, vital signs were only collected on these days if indicated. The tables and listing described in this section will only include vital signs collected in clinic on the Vital Signs eCRF. Vital Signs will be graded according to the scale in [Table 6](#).

Vital signs will be tabulated by severity, time point, and treatment group for any assessment ([Table 89](#)) and for each assessment ([Table 90](#), [Table 91](#), [Table 92](#), and [Table 93](#)). Summary statistics of vital signs will be presented for each assessment by time point and treatment group ([Table 94](#), [Table 95](#), [Table 96](#), and [Table 97](#)). All vital signs will be listed by participant and time point ([Listing 14](#)).

An abbreviated physical examination will be performed at screening (Day -30 to -2), and targeted physical exams will be performed as indicated at subsequent visits. The following body systems will be assessed in the abbreviated physical exam: general appearance, skin, head and neck, lungs, heart, liver, spleen, extremities, musculoskeletal and lymph nodes; the targeted physical exam will only include the relevant body systems. All abnormal findings will be listed by participant and time point ([Listing 15](#)).

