	Day 1	x	xx	x	xx	x	xx	x	xx	x	xx	x	xx	x	xx	x	xx
	Day 2	x	xx	x	xx	x	xx	x	xx	x	xx	x	xx	x	xx	x	xx
	Day 3	x	xx	x	xx	x	xx	x	xx	x	xx	x	xx	x	xx	x	xx
	Day 4	x	xx	x	xx	x	xx	x	xx	x	xx	x	xx	x	xx	x	xx
	Day 5	x	xx	x	xx	x	xx	x	xx	x	xx	x	xx	x	xx	x	xx
	Day 6	x	xx	x	xx	x	xx	x	xx	x	xx	x	xx	x	xx	x	xx
	Day 7	x	xx	x	xx	x	xx	x	xx	x	xx	x	xx	x	xx	x	xx
	Day 8	x	xx	x	xx	x	xx	x	xx	x	xx	x	xx	x	xx	x	xx
	Maximum	x	xx	x	xx	x	xx	x	xx	x	xx	x	xx	x	xx	x	xx

Notes: N = Number of participants in the Safety Population who received the specified vaccination; Vac = Vaccination.

“Pre-Vac” is the assessment prior to vaccination (systemic symptoms only), “Post Vac” is the in-clinic assessment 30 minutes after vaccination; “Day 1” is from the memory aid completed by the participant for the day of vaccination; “Maximum” is the maximum severity reported within 7 days following vaccination.

aFever was only collected for reactogenicity on the memory aid.

bChills/shivering/sweating.

Tables with similar format:

**Table 36: Number and Percentage of Participants Experiencing Solicited Events by Symptom, Severity, Day Relative to Vaccination, and Treatment Group – Cohort 1, Vaccination 2**

**Table 37: Number and Percentage of Participants Experiencing Solicited Events by Symptom, Severity, Day Relative to Vaccination, and Treatment Group – Cohort 1, Vaccination 3**

**Table 38: Number and Percentage of Participants Experiencing Solicited Events by Symptom, Severity, Day Relative to Vaccination, and Treatment Group – Cohort 1, Any Vaccination**

**Table 39: Number and Percentage of Participants Experiencing Solicited Events by Symptom, Severity, Day Relative to Vaccination, and Treatment Group – Cohort 2, Vaccination 1**

---

**Table 40:** Number and Percentage of Participants Experiencing Solicited Events by Symptom, Severity, Day Relative to Vaccination, and Treatment Group – Cohort 2, Vaccination 2

**Table 41:** Number and Percentage of Participants Experiencing Solicited Events by Symptom, Severity, Day Relative to Vaccination, and Treatment Group – Cohort 2, Vaccination 3

**Table 42:** Number and Percentage of Participants Experiencing Solicited Events by Symptom, Severity, Day Relative to Vaccination, and Treatment Group – Cohort 2, Any Vaccination

**Table 43:** Number and Percentage of Participants Experiencing Solicited Events by Symptom, Severity, Day Relative to Vaccination, and Treatment Group – Cohort 3, Vaccination 1

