Participants are counted once per time point.							
a Cohort 1 was enrolled and completed follow-up under v4.0 of the protocol which required collection of vital signs at this time point which was not required beginning in v5.0 of the protocol.							
b Indicates the maximum severity experienced by each participant at any time point post first vaccination, including unscheduled assessments.							

Table with similar format:

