## 16.2.7 Adverse Events

### Listing 9: Solicited Events – Systemic Symptoms

*[Implementation Note: In the “Vaccination Number (Study Day)” column, display the vaccination number followed by the actual study day the vaccination was received in parentheses, e.g., “Vac 1 (Day 1)”. The “Severity” column for Fever should include the measurement in parentheses after the result, e.g., “Mild (100.7° F)”. Include both pre- and post-vaccination assessments. For the “Day Relative to Vaccination” column, the day should be relative to the specified vaccination number; “Pre-Vac” is the pre-vaccination assessment, “Post Vac” is the in-clinic assessment 30 minutes after vaccination, and Day 1 is from the memory aid completed by the participant for the day of vaccination. For events ongoing past Day 8, the “Vaccination Number (Study Day)” and “Day Relative to Vaccination” columns should include the days of start (beyond Day 8 post-vaccination) and end, e.g., (Day 9 – Day 12); the “Severity” column will be the maximum severity (and measurement if applicable) during that time period. Include all solicited events from the Treatment Administration Record and Solicited Events eCRFs and temperatures collected on the Vital Signs eCRF within 7 days of each vaccination. In the CSR, Participant ID should be USUBJID (not PATID) for purposes of de-identification. Sort by Treatment Group, Participant ID, Vaccination Number, Day Relative to Vaccination, and Symptom. Note that the values in the table are meant to represent possible values expected for that column and are not necessarily associated with entries in other columns in the same row.]*

Treatment Group	Participant ID	Vaccination Number (Study Day)	Day Relative to Vaccination	Assessment a	Symptom	Severity	Attributed to Alternate Etiology? b
1 µg CJCV2	EHD.XXXXX	Vac 1 (Day 1)	Pre-Vac	MA	Arthralgia	None	Yes: [alternate etiology]
1 µg CJCV2+ALFQ		Vac 1 (Day 1)	Post Vac	Clinic	Fatigue	Mild	No
3 µg CJCV2		Vac 1 (Day 1)	Day 1		Fever	Moderate	N/A
3 µg CJCV2+ALFQ		Vac 1 (Day 2)	Day 2		Feverishness	Severe	
10 µg CJCV2		Vac 1 (Day 3)	Day 3		Headache	[Severity] (XXX.X° F)	
10 µg CJCV2+ALFQ		Vac 1 (Day 4)	Day 4		Malaise		
		Vac 1 (Day 5)	Day 5		Myalgia		
		Vac 1 (Day 6)	Day 6		Nausea		
		Vac 1 (Day 7)	Day 7		Vomiting		
		Vac 1 (Day 8)	Day 8				
		Vac 1 (Day 9 – Day X)	Day 9 – Day X				
		Vac 2 (Day 29)	Pre-Vac				
		Vac 2 (Day 29)	Post Vac				

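### Solicited fever counts clinic temperatures that were required 48 hours after each dose only in Cohort 1, so fever is ascertained slightly differently across doses; a common-source sensitivity row and a corrected footnote are needed

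*SAP*

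**What the plan says.** **The fever rule.** SAP 9.3.1: "Temperatures collected on the Vital Signs eCRF within 7 days following vaccination will be considered towards the solicited AE of fever". The same sentence says that they "will be included in all tables, figures, and listings summarizing solicited AEs". The implementation note to Listing 9 repeats the rule, asking for "temperatures collected on the Vital Signs eCRF within 7 days of each vaccination". The vital-sign paragraph of SAP 4.5.1, footnote a of Table 6 and the note to Table 31 agree with it.

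**The collection schedule.** SAP 9.7 says that Cohort 1 completed follow-up under protocol v4.0, "which also required collection of vital signs at Day 3, Day 15, Day 31, Day 43, Day 59, and Day 71". It continues: "in the later versions of the protocol followed by Cohorts 2 and 3, vital signs were only collected on these days if indicated". A footnote to Table 89, repeated under Tables 91 and 94, describes v4.0 as the version "which required collection of vital signs at this time point which was not required beginning in v5.0 of the protocol".

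**Cohort and dose.** SAP 4.4.5: "A fixed dose of CJCV2 will be used for each cohort", namely 1, 3 and 10 µg in Cohorts 1, 2 and 3.

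**The table footnote.** Footnote a of Table 35, whose shell is reused for Tables 36-46, reads: "Fever was only collected for reactogenicity on the memory aid".

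**The concern.** Solicited events through 7 days after each vaccination are a primary endpoint, and the primary objective is the safety of three doses with and without ALFQ. Fever is one of the solicited events and also feeds the any-systemic-symptom row. Days 3, 31 and 59 all fall within 7 days of a dose, so a temperature taken then counts as solicited fever. That reading was routine at the lowest dose and discretionary at the two higher doses. Cohort and dose coincide, so a reader who compares fever across doses compares slightly different detection schemes.

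The SAP already deals with this in the vital-sign tables. Table 89 prints those days for the 1 µg groups only, Table 94 shows them as not applicable for the other groups, and both carry a footnote on the protocol version. The same temperatures pass into the solicited-fever tables without any such note.

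The footnote is a second, smaller matter. It tells the reader of Tables 35-46 that fever came from the memory aid alone, while the rule puts clinic temperatures into those tables.

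**Working it through.** **1. The plan's own precision figure.** SAP section 5 gives an exact 95% interval of 0-31% for no events in 10 participants. The Clopper-Pearson upper limit is 1 − 0.025^(1/10) = 30.85%, which rounds to 31%. The figure reproduces.

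**2. Scheduled post-dose temperatures inside the 7-day window.** Inputs: memory-aid Days 1-8 from the Table 35 shell (8 readings per dose), and clinic readings from SAP 9.7 and the SAP Table 2 schedule, taken at their nominal days.

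| | Memory aid per dose | Clinic, 48 h | Clinic, 7 days | Total per dose | Over 3 doses |
|---|---|---|---|---|---|
| Cohort 1 (1 µg) | 8 | 1 | 1 | 10 | 30 |
| Cohorts 2 and 3 (3, 10 µg) | 8 | 0 scheduled | 1 | 9 | 27 |

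The difference is one reading in ten per dose, or three per participant. Over 20 participants that is at most 3 × 20 = 60 scheduled readings in Cohort 1. Cohorts 2 and 3 also have an unknown number of readings taken if indicated, and these count towards fever as well.

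**3. What one extra event does to a group of 10.** The exact interval for 0/10 is 0-30.8%; for 1/10 it is 0.3-44.5%.

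**4. Illustration only.** The documents give no rate for fevers found at the 48-hour clinic reading and missed by every other source. Let q be that rate per dose, assumed independent across doses and participants. The proportion of participants who gain a fever over three doses is 1 − (1 − q)^3. The chance of at least one such participant in a group of 10 is 1 − (1 − q)^30.

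| q (assumed) | Participants gaining a fever | Expected per group of 10 | Chance of at least one in 10 |
|---|---|---|---|
| 1% | 3.0% | 0.3 | 26% |
| 2% | 5.9% | 0.6 | 45% |
| 5% | 14.3% | 1.4 | 79% |

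These rows show how sensitive groups of 10 are to a single reading. They do not estimate a bias in this trial.

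**5. Direction.** Taken alone, the scheduled 48-hour reading gives Cohort 1 more chance to record a fever. The readings taken if indicated in Cohorts 2 and 3 add to fever detection there and may be partly prompted by symptoms. Their number and timing are not stated, so the net direction cannot be derived.

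**6. Effect of a common-source definition.** With the memory aid plus the scheduled 7-day clinic reading, every cohort has 8 + 1 = 9 scheduled readings per dose.

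**The case against.** The strongest reply is that the gap hardly matters. To change a count, a participant must be febrile in clinic at about 48 hours yet show no fever on any memory-aid reading or at the 7-day visit. Protocol 3.1.2 describes systemic reactions to ALFQ in the malaria vaccine trials as lasting 24-36 hours, so a 48-hour reading may come after the likely fever. The any-systemic-symptom row changes only for someone with no other systemic symptom. The analysis is descriptive, the solicited tables are separate by cohort, and the cohorts already differ in eligibility (SAP 4.3). Listing 9 marks each result as memory aid or clinic, and Table 90 shows clinic temperatures. All of this stands, and it keeps the point modest. It does not remove it: readers will compare fever across doses in a dose-escalation trial, and nothing in the fever tables warns them.

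A second reply concerns the remedy. In-window temperatures are not reported as unsolicited events (SAP 4.5.1; Table 6). If the main fever definition excluded the Day 3, 31 and 59 readings, a fever measured only then would be in neither the main solicited fever count nor the unsolicited tables of a first-in-human trial. This stands, and it is why the all-source row should remain the main one.

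A third reply is that the footnote only explains why fever has no Post Vac row in Table 35. That is the likely intent, and the shell's Pre-Vac fever row fits it. The wording still contradicts 9.3.1 and needs correction, but the problem is editorial.

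A reader might also infer that Cohorts 2 and 3 had no 48-hour clinic temperatures. The documents support only that none were scheduled. Protocol 5.3.1 still lists vital signs at the 3-day visit, as applicable and in clinic or virtually, whereas Protocol Appendix A schedules none there. Those two places should be reconciled.

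**Conclusion.** The point holds in a limited form. Solicited fever draws on a clinic reading that was required at one dose and discretionary at the other two. Comparisons of fever across doses therefore rest on about 10 against 9 scheduled readings per dose. That count assumes complete memory aids and visits on their nominal days. The effect is probably small, and neither its size nor its net direction follows from the documents.

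Two stronger readings are tempting and are not supported. One is that Cohort 1 fever will be inflated by some number of percentage points. Any such figure depends on an assumed pick-up rate for which the documents give no basis. The other is that the ALFQ comparison is distorted. Both arms of a cohort followed the same schedule and were assessed blind, so that comparison is unaffected.

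**What to change.** 1. Keep the all-source rule of SAP 9.3.1 as the main fever row.
2. Add to Tables 32-34 a sensitivity row for fever, and one for any systemic symptom, using only sources scheduled in all cohorts: memory-aid temperatures plus the scheduled 7-day post-dose clinic reading.
3. Footnote those tables with the protocol-version difference at Days 3, 31 and 59, as Tables 89, 91 and 94 already do.
4. Reword footnote a of Table 35, and of the tables that reuse its shell, to say that fever has no 30-minute Post Vac assessment and that in-window Vital Signs eCRF temperatures are included.

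The cost is a few table rows, one data filter and two footnotes. No data collection changes, and no observed fever leaves the main tables.
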